2.4.6 Analyses of pharmacokinetic variables

Plasma concentrations of sotagliflozin and its 3-O-glucuronide metabolite will be summarized by visit and nominal sampling time (pre-dose at Weeks 4, 18, 26, 39, and 52 and 3 hours post-dose at Week 26 and Week 52) in the PK population (see Section 2.3.3) in the sotagliflozin group, using descriptive statistics such as number, geometric mean, coefficient of variation, median, minimum and maximum. Individual plasma concentrations of sotagliflozin and its 3-O-glucuronide metabolite at nominal sampling times will also be listed.

2.5 DATA HANDLING CONVENTIONS**2.5.1 General conventions**

The following formulas will be used for computation of parameters.

HbA1c

The formula to convert HbA1c from Diabetes Control and Complications Trial (DCCT) aligned value to International Federation of Clinical Chemistry and Laboratory Medicine (IFCC) standardized value is,

$$\text{IFCC-HbA1c (mmol/mol)} = [\text{DCCT-HbA1c (\%)} - 2.15] \times 10.929.$$

Renal function formulas

The estimated GFR (mL/min/1.73 m²) will be calculated using the 4 variable Modification of Diet in Renal Disease (MDRD) formula:

$$\text{Standard unit: eGFR (mL/min/1.73 m}^2\text{)} = 175 \times [\text{Serum Creatinine } (\mu\text{mol/L})/88.4]^{-1.154} \times \text{Age (year)}^{-0.203} \times 1.212 \text{ (if Black)} \times 0.742 \text{ (if female)}$$

$$\text{Conventional unit: eGFR (mL/min/1.73 m}^2\text{)} = 175 \times \text{Serum Creatinine (mg/dL)}^{-1.154} \times \text{Age (year)}^{-0.203} \times 1.212 \text{ (if Black)} \times 0.742 \text{ (if Female)}$$

UACR

$$\text{Standard unit: UACR (mg/g)} = \text{Urine Albumin (mg/dL)} / [\text{Urine Creatinine (mmol/L)} \times 11.31] \times 1000$$

$$\text{Conventional unit: UACR (mg/g)} = \text{Urine Albumin (mg/dL)} / \text{Urine Creatinine (mg/dL)} \times 1000$$

UGCR

$$\text{Standard unit: UGCR} = \text{Urine Glucose (mmol/L)} / \text{Urine Creatinine (mmol/L)}$$

$$\text{Conventional unit: UGCR} = \text{Urine Glucose (mg/dL)} / \text{Urine Creatinine (mg/dL)}$$

Calculation of LDL-C

When TG is lower than or equal to 4.52 mmol/L (400 mg/dL), LDL-C is calculated using the Friedewald equation as:

- in standard unit (mmol/L), $\text{TC} - \text{HDL-C} - \text{TG}/2.17$;
- in conventional unit (mg/dL), $\text{TC} - \text{HDL-C} - \text{TG}/5$.

2.5.2 Data handling conventions for secondary efficacy variables

Scheduled measurements (see Section 2.5.4) of continuous efficacy variables collected during the study will be used in the analyses including those obtained after IMP discontinuation or introduction of rescue therapy. Continuous secondary efficacy endpoints will be analyzed with missing values imputed by the retrieved dropouts & washout imputation method or by the control-based copy reference imputation method according to the criterion described in Section 2.4.4.1.

For the categorical secondary efficacy endpoints, data handling conventions are described in Section 2.4.4.2.

2.5.3 Missing data

For categorical variables, patients with missing data are not included in calculations of percentages unless otherwise specified. When relevant, the number of patients with missing data is presented.

Derived variables will be considered missing if any of the original variables required to calculate them are missing. For example, if either a baseline assessment or an endpoint assessment is missing for a particular patient, then change from baseline at endpoint will be missing. Depending upon the assessment, analyses may not include all patients in the analysis population, because certain patients in the intended population may have missing data.

Incomplete date of first administration of double-blind IMP

Date/time of first administration is the first non-missing start date/time of double-blind IMP completed in the e-CRF “First dose IMP” module.

For patients who are randomized and dispensed a double-blind treatment kit but who are lost to follow-up just after Visit 3 (eg. only the treatment kit number is reported in the e-CRF “Exposure - treatment period” module without any dose information), the date of first administration will be imputed using the date of randomization. When a patient is randomized but not exposed, “Not taken” should be ticked in the e-CRF “First dose IMP” module.

Handling of computation of treatment duration if investigational medicinal product end of treatment date is missing.

For the calculation of the treatment duration, the date of the last dose of IMP is equal to the date of last administration reported on the on the e-CRF “Treatment status library” page. If this date is missing, the exposure duration should be left as missing.

The last dose intake should be clearly identified in the case report form and should not be approximated by the last returned package date.

Handling of medication missing/partial dates

No imputation of medication start/end dates or times will be performed. If a medication date or time is missing or partially missing and it cannot be determined whether it was taken prior or concomitantly, it will be considered a prior, concomitant, and posttreatment medication.

Handling of adverse events/hypoglycemia with missing or partial date/time of onset

Missing or partial adverse event onset dates and times will be imputed so that if the partial adverse event onset date/time information does not indicate that the adverse event started prior to treatment or after the treatment-emergent adverse event period, the adverse event will be classified as treatment-emergent. No imputation of adverse event end dates/times will be performed. These data imputations are for categorization purpose only and will not be used in listings. No imputation is planned for date/time of adverse event resolution.

Handling of adverse events/hypoglycemia when date and time of first investigational medicinal product administration is missing

When the date and time of the first IMP administration is missing, the day of randomization should be considered as the start date of TEAE period (see Section 2.1.4). The exposure duration should be kept as missing.

Handling of adverse events/hypoglycemia when IMP end of treatment date is missing

For the purpose of defining TEAE period, the date of the last administration of double-blind IMP is equal to the date of the last administration reported on the e-CRF "Treatment Status Library" page.

If the date of last administration reported on the e-CRF "Treatment Status Library" page is

- Partially missing, it will be imputed with a date as late as possible before or on the date of last available information on e-CRF "Completion of End of Study/Follow-up".
- Completely missing, it will be imputed with the date of last available information on e-CRF "Completion of End of Study/Follow-up" page.

If the date of last available information on e-CRF "Completion of End of Study/Follow-up" page is:

- Partially missing, it will be imputed with a date as late as possible.

Completely missing, all adverse events occurred on or after the first administration of double-blind IMP will be considered as treatment emergent adverse events.

Handling of missing assessment of relationship of adverse events to IMP

If the assessment of the relationship to IMP is missing, then the relationship to IMP has to be assumed and the adverse event considered as such in the frequency tables of possibly related adverse events, but no imputation should be done at the data level.

Handling of missing severity/grades of adverse events

If the severity/grade is missing for 1 of the treatment-emergent occurrences of an adverse event, the maximal severity on the remaining occurrences will be considered. If the severity is missing for all the occurrences, a “missing” category will be added in the summary table.

Handling of potentially clinically significant abnormalities

If a patient has a missing baseline he will be grouped in the category “normal/missing at baseline.”

For PCSAs with 2 conditions, one based on a change from baseline value or a normal range and the other on a threshold value, with the first condition being missing, the PCSA will be based only on the second condition.

For a PCSA defined on a threshold and/or a normal range, this PCSA will be derived using this threshold if the normal range is missing; eg, for eosinophils the PCSA is >0.5 GIGA/L or $>ULN$ if $ULN \geq 0.5$ GIGA/L. When ULN is missing, the value 0.5 should be used.

Measurements flagged as invalid by the laboratory will not be summarized or taken into account in the computation of PCSA values.

Linked adverse events that worsened or became serious

An AE that worsened or became serious will have a separate record in the data from the original event record with an AE identification number that links the new record to the original record. An AE that worsened or became serious will be considered a new recurring AE in the summary of recurrent events or in the summary of events by time intervals.

Handling of missing data for continuous efficacy endpoints

Please see Section 2.4.4.1 and Section 2.4.4.2.

Handling of missing data for categorical secondary efficacy endpoints

Please see Section 2.4.4.2.

2.5.4 Windows for time points

The following steps will decide how the scheduled and/or unscheduled visits will be used in the analyses on efficacy variables and the by-visit summaries for safety variables (clinical laboratory data in Section 2.1.4.4 and vital signs in Section 2.1.4.5).

Step 1 A scheduled measurement will be used if it is available; otherwise, an unscheduled measurement (including the end of treatment/study visit for those prematurely discontinued) will be used if it happens to be on the same date as the date of the scheduled visit.

Step 2 After Step 1, if there are still no measurement for a given parameter at a scheduled visit, the analysis window below (Table 4) will be applied to re-allocate a post-baseline unscheduled measurement to a scheduled measurement.

Table 4 - Analyses window definition

Scheduled visit post baseline	Targeted study day	Analysis window in study days
Week 1 (Visit 4)	7	2 to 10
Week 2 (Visit 5)	14	11 to 17
Week 3 (Visit 6)	21	18 to 24
Week 4 (Visit 7)	28	25 to 41
Week 8 (Visit 8)	56	42 to 69
Week 12 (Visit 9)	84	70 to 104
Week 18 (Visit 10)	126	105 to 153
Week 26 (Visit 11)	182	154 to 227
Week 39 (Visit 12)	273	228 to 318
Week 52 (Visit 13)	364	≥319

Study days are calculated from the day of first administration of double-blind IMP; the day of first administration of IMP (or the day of randomization if not exposed) is Day 1.

After applying the above time windows, if multiple assessments are associated to the same time point, the closest from the targeted study day will be used. In case of equality, the last measurement will be used. Re-allocated scheduled visits (ie, visit numbers) should be sequential if ordered by the date of measurement.

After Step 2, if there are still no measurement for a given parameter at a scheduled visit, data is considered missing for efficacy analyses, where multiple imputation would be applied as appropriately as described in [Section 2.4.4](#).

Reference day

The reference day for the calculation of extent of exposure, time to onset, and relative days will be the day of the first administration of double-blind IMP or the day of randomization if not exposed to double-blind IMP, denoted as Day 1.

Baseline definition for efficacy/safety data

For the safety analyses, the baseline for a given parameter is defined as the last available measurement (or the average of all measurements for creatinine and eGFR), including unscheduled assessments, assessed prior to the first administration of double-blind IMP. For the efficacy analyses, the baseline for a given parameter is defined as the last available measurement (or the average of all measurements for creatinine and eGFR), including unscheduled assessments, assessed prior to the first administration of double-blind IMP or the last available value (or the

average of all measurements for creatinine and eGFR) before randomization if not treated with double-blind IMP.

Summary statistics by visit for continuous efficacy endpoints

Summary statistics (number, mean, SD, SE, minimum, median, maximum) of continuous efficacy endpoints (observed data and change from baseline) will be provided at scheduled visits as per protocol. Summaries showing data by visit will be presented according to the visit number (or re-allocated visit number, see Section 2.5.4) and labeled with the targeted approximate day/week.

Last on-treatment value for laboratory variables and vital signs

The last on-treatment value is the final measurement assessed during the treatment epoch, regardless of the introduction of rescue therapy, including measurements at unscheduled visits. Please see details in [Section 2.1.4](#) and [Section 2.4.5](#).

Display of safety data by visit (laboratory variables and vital signs)

Descriptive statistics (number, mean, SD, minimum, median, maximum) of quantitative laboratory variables and vital signs (observed data and change from baseline) during the TEAE period will be provided at scheduled visits. In addition, these summaries will also include a row for the 'last value on-treatment' to describe the last available on-treatment value (see above). Summaries showing data by visit will be presented according to the visit number (or re-allocated visit number, see [Section 2.5.4](#)) and labeled with the targeted approximate day/week.

As specified in the study protocol, laboratory data from scheduled visits are reported by central laboratories. The local results will not be used in the efficacy analyses or in the definition of baseline for both safety and efficacy analyses. In the safety analyses, for parameters with PCSA defined based on normal range, local results will be used in the PCSA summary if they are accompanied by a local laboratory normal range. For parameters with PCSA not defined based on normal range, local results will be used in the PCSA summary as appropriate.

When a patient has more than 1 measurement from the central laboratory for the same laboratory parameter on the same date, the average of the measurements will be used. For the same laboratory parameter, if a patient has more than 1 measurement on different dates for the same scheduled visit, the value closest to the date of the visit will be used for the scheduled visit. When the values for the same scheduled visit are equidistant, the last value should be used for the scheduled visit. Similar rules will be applicable to a patient who has more than 1 set of measurements for the same vital sign parameter (ie, SBP, DBP, or HR) on the same date.

26-week double blind core treatment period

The 26-week double-blind core treatment period is the time from first administration of double-blind IMP to the last administration of double-blind IMP on or before Visit 11 (Week 26) (or Day 182 if Visit 11 (Week 26) date is missing). This is for defining EOT status at Week 26 and analyzing selected efficacy parameters (eg, rescued patients) during the core treatment period.

TEAE period for the 26-week double blind core treatment period

The TEAE period for the 26-week double-blind core treatment period is (1) the time from the first administration of the double-blind IMP up to 15 days (1 day for hypoglycemia) after the last administration of IMP if the patient discontinued treatment on or before Visit 11 (or Day 182 if Visit 11 date is missing), or (2) the time from the first administration of the double-blind IMP to the administration at Visit 11 (Week 26) (or Day 182 if Visit 11 (Week 26) date is missing) if the patient remained treated beyond Visit 11 (Week 26). This is for the purpose of safety analyses during the core treatment period.

26-week core study period

The 26-week core study period is the time from first administration of double-blind IMP to Visit 11 (Week 26) (or Day 182 if Visit 11 (Week 26) date is missing) or the end of TEAE period for the 26-week double-blind core treatment period (as defined above) whichever is later. This is for defining EOS status at Week 26.

Time to event analysis

For time to event analysis/KM plot, time to event (eg, treatment discontinuation, rescue therapy, hypoglycemia, ESRD, etc) is defined as the number of days from the date of the first administration of double-blind IMP (or the date of randomization if not exposed) to the start date of the first occurrence of the event during the respective analysis period.

Patients who did not experience any event during the respective analysis period are considered censored observations. The censoring rules are defined below.

Time to event	Censoring date at Week 26 (1st step analysis)	Censoring date at EOT/EOS (2nd step analysis)
Treatment discontinuation due to any reason	Not applicable	EOT
Treatment discontinuation due to AE	Not applicable	EOT
Time to rescue	min (EOT, Date of W26 visit)	EOT
Time to severe or documented hypoglycemia	See Section 3	Min (EOT+1, EOS)
Time to ESRD	min (EOS, Date of W26/re-allocated W26 eGFR value)	EOS
Time to eGFR decrease	min (EOS, Date of W26/re-allocated W26 eGFR value)	EOS
Time to UACR progression/improvement	min (EOS, Date of W26/re-allocated W26 UACR value)	EOS

Note: (1) Day 182 will be used if Date of Week 26 visit (or date of W26/re-allocated W26) is not available.
(2) Date of EOS will be used if date of EOT is not available; Last contact date will be used if date of EOS is not available.

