#### **10.1.2.4 On-site Visit 11 (Week 26)**

The following procedures will be performed at this visit:

- Measurement of body weight
- Vital signs. After 5 minutes resting, seated SBP, DBP, and HR will be assessed 3 times with at least 1 minute between each measurement (see [Appendix C](#) for details)
- Complete physical examination
- Diet and exercise instruction
- Instruction on DKA symptoms and basic GU hygiene and hydration (see [Appendix B](#)) is provided
- IRT to be notified IMP for re-supply
- Patient diary is collected/reviewed and a new diary is dispensed. Instructions/training are provided as needed
- IMP is dispensed
- IMP accounting and compliance for double-blind IMP
- Concomitant medications are assessed
- Fasting SMBG is assessed
- 12-lead ECG
- The following laboratory testing (by the central laboratory):
  - Fasting plasma glucose
  - HbA1c

- Fructosamine
  - Clinical chemistry (including amylase, lipase, uric acid) and hematology
  - Cystatin C
  - NT-proBNP
  - Fasting lipids
  - Urine pregnancy testing for WOCBP
  - Urinalysis (dipstick and microscopy)
  - Collection of home urine for albumin, protein, creatinine, calcium, phosphorus, magnesium, glucose and albumin:creatinine ratio
  - Additional laboratory testing at this visit:
    - Pre-dose PK (plasma concentration sample for sotagliflozin and sotagliflozin-3-O-glucuronide); an additional blood sample will be collected 3 hours after IMP administration for the assessment of creatinine (for eGFR) and for assessing plasma concentration of sotagliflozin and sotagliflozin-3-O-glucuronide
    - Markers of intestinal transit and absorption (vitamins B6, B12, K, E, and A, serum folate, and ferritin)
    - Markers of bone and calcium metabolism (serum calcium, serum 25-hydroxyvitamin D, serum 1,25-dihydroxyvitamin D, serum magnesium, serum phosphorus, serum PTH, markers of bone resorption [serum NTX, serum  $\beta$ -CTX-1], and bone formation [serum P1NP]), osteocalcin, and ALP
- █
- Patients are evaluated for glycemic rescue (see [Section 8.2](#))
  - Evaluate for 50% increase in creatinine
  - AEs/SAEs/AESI/EOSI and hypoglycemia (if any) are reported
  - Patients are instructed to return to the site in the fasting state for Visit 12 (Week 39)
  - For accountability and compliance purposes, patients are instructed to return to the site with all their used, in-use and not used treatment kits(s) dispensed during visit 10

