2.1.4 Safety endpoints

The safety analysis will be based on the reported adverse events, hypoglycemia, acute renal failure and other safety information, such as clinical laboratory data, vital signs, electrocardiogram (ECG), physical examination and marker of intestinal transit and absorption, markers of bone and calcium metabolism, etc.

Observation period

The observation period will be divided into 4 epochs:

- The **screening** epoch is defined as the time from the signed informed consent date up to the first administration of the double-blind IMP.
- The **treatment** epoch is defined as the time from the first administration of double-blind IMP to the last administration of double-blind IMP. This epoch includes the 26-week double-blind core treatment period and the 26-week double-blind extension treatment period. The 26-week core treatment period is the time from the first administration of double-blind IMP to the last administration of double-blind IMP on or before Visit 11 (Week 26) [or Day 182 if Visit 11 (Week 26) date is missing].
- The **residual treatment** epoch is defined as the time from the last administration of the IMP to the last administration of the IMP + 15 days (1 day for hypoglycemia).

The treatment-emergent adverse event (TEAE) period will include both **treatment** and **residual treatment** epochs (See the TEAE period for the 26-week core treatment period in [Section 2.5.4](#)).

- The **posttreatment** epoch is defined as the period of time starting the day after the end of the treatment-emergent adverse event period up to the last protocol-planned visit or the resolution/stabilization of all serious adverse events (SAE), adverse events of special interest (AESI) and events of special interest (EOSI), whichever is later.

The on-study observation period is defined as the time from start of double-blind treatment until the end of the study (defined as the last scheduled visit for those who completed the study and the date collected on e-CRF page “Completion of End of Study/Follow-up” for those who did not complete the study).

The post-study observation period is defined as the time from the day after the end of the study until the resolution/stabilization of all SAE, AESI and EOSI if applicable.

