- For quantitative safety parameters based on central laboratory/reading measurements, descriptive statistics will be used to summarize results and change from baseline values by visit and treatment group for the 52-week entire treatment period only. Summaries will include the last on-treatment value. The last on-treatment value is commonly defined as the value collected at the same day/time of the last administration of IMP for the 52-week entire treatment period. If this value is missing, this last on-treatment value will be the closest value prior to the last administration of IMP during the 52-week entire treatment period.
- The analysis of the safety variables will be essentially descriptive and no systematic testing is planned. Relative risks versus placebo and their 95% CIs may be provided, if relevant.
- Selected safety analyses will be summarized by age, gender, racial subgroups, and other pertinent subgroups (see details in [Section 2.4.5.1](#) and [Section 2.5.2](#)).

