2.4.5.4 Analyses of laboratory variables

Laboratory parameters will be grouped and summarized by biological function as described in Section 2.1.4.4.

The summary statistics (including number, mean, median, Q1, Q3, standard deviation, minimum and maximum) of all laboratory variables (central laboratory values, changes from baseline, and/or percent change from baseline [eg, lipid parameters, albumin, total protein, hemoglobin, hematocrit]) will be calculated for each applicable visit or study assessment (screening, baseline, postbaseline time point, last on-treatment value) by treatment group. Graphical presentations may be used to examine trends over time using mean (\pm SE) and/or mean change from baseline (\pm SE) at scheduled visits (eg, creatinine, eGFR).

The incidence of PCSAs (list provided in Appendix B) at any time during the treatment-emergent adverse event period will be summarized by biological function and treatment group whatever the baseline level and/or according to the following baseline status categories:

- Normal/missing
- Abnormal according to PCSA criterion or criteria

For creatinine, $\geq 50\%$ change from baseline will be provided in addition to the PCSA criteria defined, ie, $\geq 150 \mu\text{mol/L}$ (Adults), $\geq 30\%$ change from baseline, $\geq 50\%$ change from baseline, and $\geq 100\%$ change from baseline. For eGFR, $\geq 50\%$ decrease from baseline will be provided in

addition to the PCSA criteria defined, ie, <15 (end stage renal disease), ≥ 15 - <30 (severe decrease in GFR), ≥ 30 - <60 (moderate decrease in GFR), ≥ 60 - <90 (mild decrease in GFR), and $\geq 50\%$ decrease from baseline. For parameters for which no PCSA criteria are defined, similar tables using the normal range will be provided.

All measurements collected during the TEAE period, including values from unscheduled visits, will be considered for the PCSA summaries. These summaries will include patients in the safety population who have at least 1 assessment performed during the TEAE period. When a PCSA definition involves a change from baseline value, patients must also have a baseline value to be included in the summaries, and when required by the definition of the abnormality, patients must also have available laboratory normal ranges.

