- d The abbreviated physical exam should focus on cardiac and respiratory systems, as well as any areas important for assessment of AEs if necessary.
- e Additional visit (recheck creatinine) from visit 8 every 2 weeks, contact IRT for treatment allocation if applicable.
- f Self-monitored blood glucose (SMBG) is to be performed fasting, at least 3 times per week from start of Run-in until end of Treatment Period including on day of each on-site study visit except Visits 4 and 5. Patients will also be requested to self-assess blood glucose levels whenever they experience symptoms of hypoglycemia. SMPG ≤70 mg/dL (3.9 mmol/L) will be documented on the hypoglycemia e-CRF. The SMBG will be presented as equivalent self-monitoring plasma glucose (SMPG).
- g The 12-lead ECG recordings should be obtained prior to IMP administration. The ECG will be evaluated as "normal" or "abnormal".

Statistical Analysis Plan

Version: Final 3.0

Lexicon Pharmaceuticals Protocol No. EFC15166

Date of Issue: 21 November 2019

Covance Study ID: 000000155203

- h* All laboratory assessments occur prior to dose of double-blind IMP. All visit dates will be scheduled based on the date of randomization with a ± 5 days visit window allowed during the treatment period.
- i* Safety laboratory will include hematology and clinical chemistry, please see the list in Table 2 in protocol. Other clinical chemistry tests will include amylase and lipase.
- j* Serum pregnancy testing only at screening; urine pregnancy testing subsequently. Serum pregnancy test results must be reviewed prior to beginning the Run-in Phase for all women of childbearing potential (WOCBP) unless there is documented history of menopause (based on documented follicle-stimulating hormone [FSH] and estradiol levels – if results not documented then FSH and estradiol will be tested at Screening Visit) or they are surgically sterile. Any positive urine test results must be confirmed based on serum pregnancy test. The Investigator may perform additional tests at their discretion or as required by local regulations.

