- k* Plasma concentration samples for sotagliflozin and sotagliflozin-3-O-glucuronide collected on Weeks 4, 18, 26, 39, and 52 may be drawn with the other laboratory assessments but MUST be collected before administration of IMP. The time of the last intake of study drug prior to visits where PK samples are taken should be recorded by the patient in the patient diary. Patients should be reminded of this at visits preceding PK time points to ensure these details are captured. In the case of premature IMP discontinuation, PK samples should not be drawn at the premature EOT visit, neither at all subsequent visits.
- l* An additional blood sample will be drawn at Weeks 26 and 52 Visits at 3 hours after administering the dose of IMP for creatinine (for eGFR) and for assessing plasma concentration of sotagliflozin and sotagliflozin-3-O-glucuronide.
- m* The markers of intestinal transit and absorption include vitamins B6, B12, K, E, and A, serum folate, and ferritin.
- n* Markers of bone and calcium metabolism :serum calcium , serum 25-hydroxyvitamin D, serum 1,25-dihydroxyvitamin D, serum phosphorus , serum magnesium, serum parathyroid hormone (iPTH), markers of bone resorption (serum NTX, serum β -CTX-1), bone formation (serum P1NP and osteocalcin) and serum alkaline phosphatase.
- o* Urinalysis includes urine dipstick and microscopy. Dipstick includes assessment of specific gravity, pH, protein, blood, ketones, bilirubin, urobilinogen, nitrate, and leukocyte esterase. Microscopy includes but is not limited to detection of formed cellular elements, casts, bacteria, yeast, parasites, and crystals in centrifuged urine sediment. In the event of abnormal urinalysis findings suspicious of urinary tract infection (UTI), urine culture should be performed. Positive urine culture determination will be based upon the criteria of the reporting laboratory. Additionally, urine cultures should be performed if at any point the PI suspects the presence of a UTI.

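### The same-date averaging rule makes no exception for the planned 3-hour post-dose creatinine, so by-visit creatinine at Weeks 26 and 52 mixes sampling conditions for patients who give both samples

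*SAP*

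**What the plan says.** **The averaging rule.** SAP 2.5.4, under the by-visit display of safety data, deals with repeated central-laboratory results: "for the same laboratory parameter on the same date, the average of the measurements will be used". No exception is stated for samples planned at different times relative to dosing.

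**The second sample.** Footnote l of SAP Appendix E plans an "additional blood sample will be drawn at Weeks 26 and 52 Visits at 3 hours after administering the dose of IMP for creatinine". Footnote l of the protocol flow chart (1.2) and the visit procedures in protocol 10.1.2.4 (Week 26) and 10.1.3.2 (Week 52) say the same, and give eGFR as the purpose. Footnote h of Appendix E states the general rule: "All laboratory assessments occur prior to dose of double-blind IMP". Baseline creatinine and eGFR are averages of values before the first double-blind dose (SAP 2.1.1 and 2.5.4).

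**The outputs.** SAP 2.5.4 says that descriptive statistics "of quantitative laboratory variables and vital signs (observed data and change from baseline) during the TEAE period will be provided at scheduled visits". SAP 2.4.5 produces these summaries "by visit and treatment group for the 52-week entire treatment period only". The TEAE period ends with the residual treatment epoch, which runs "from the last administration of the IMP to the last administration of the IMP + 15 days" (SAP 2.1.4). SAP 2.4.5.4 names creatinine and eGFR as examples of parameters for trend graphs.

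**The contrast with PK.** Plasma concentrations from the same 3-hour draw are summarised by visit and by nominal sampling time (SAP 2.4.6). Creatinine has no matching rule.

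**The concern.** At two visits, patients dosed there are planned to have two creatinine results on one date under different conditions. The only rule that addresses same-date results merges them. A trend plot would then compare pre-dose values at most visits with mixed values at Weeks 26 and 52, and part of any acute post-dose change could look like a change over time in renal function.

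Patients who have stopped IMP but still attend (protocol 10.3.4) have no post-dose draw. The two visits would therefore combine averaged and single values, in shares that may differ by arm.

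The 3-hour creatinine also has no summary of its own, so averaging hides what that sample was collected to show. In a population enrolled at eGFR 15 to below 30, the creatinine and eGFR course is a central safety display.

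**Working it through.** The plan states no figure on this point, so there is none to reproduce. The check has two parts.

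**1. Does any text keep the two samples apart?**

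- *Central laboratory:* creatinine is run there (protocol Table 2), so the averaging rule applies to it.
- *Step 1 of SAP 2.5.4* prefers a scheduled over an unscheduled measurement. Both samples are planned for the visit, so Step 1 does not choose between them.
- *Core TEAE period:* for patients who continue treatment it ends at the Visit 11 administration, which would leave out the Week 26 post-dose value. By-visit laboratory tables use the 52-week period instead, so that value is in scope. The Week 52 value is covered by the 15 days after last dose.
- *SAP 2.4.5.4* refers to post-baseline time points without separating pre-dose from 3 hours.

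No passage selects the pre-dose value.

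**2. What does averaging do?**

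Inputs: the MDRD creatinine exponent of -1.154 (SAP 2.5.1) and an acute post-dose change d in creatinine. The documents do not give d; the assumed range is -10% to +10%.

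- Averaged creatinine relative to pre-dose: (1 + (1 + d))/2 - 1 = d/2.
- eGFR from the averaged creatinine: (1 + d/2)^-1.154 - 1.
- Mean of the two eGFR values: ((1 + d)^-1.154 - 1)/2.

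| d | Creatinine shift | eGFR, creatinine averaged first | eGFR values averaged |
|---|---|---|---|
| -10% | -5.0% | +6.10% | +6.46% |
| -5% | -2.5% | +2.96% | +3.05% |
| +5% | +2.5% | -2.81% | -2.74% |
| +10% | +5.0% | -5.47% | -5.21% |

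For an affected patient with pre-dose eGFR 22, the widest shifts are 22 x 0.0646 = +1.4 and 22 x -0.0547 = -1.2 mL/min/1.73 m2. At eGFR 15 they are +1.0 and -0.8; at 30, +1.9 and -1.6.

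If a share p of patients has paired samples, the visit mean moves by about p times these amounts. With p = 0.5 (illustration only), the range is -2.5% to +2.5% for creatinine and about +3.2% to -2.7% for eGFR.

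**If the rule also reached the >50% eGFR decline counts** (SAP 2.4.4.3), the pre-dose decline at which the reported value crosses 50% would be 1 - 0.5/(1 + shift). For d = +10%, 1 - 0.5/0.9453 = 47.1%. For d = -10%, 1 - 0.5/1.0646 = 53.0%. Only patients within about 3 percentage points of the threshold could change category.

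**The case against.** **Reach to eGFR.** The averaging rule sits under the safety display. SAP 2.1.4.4 lists creatinine, but not eGFR, among safety laboratory parameters. eGFR change is an efficacy endpoint (SAP 2.1.3.3), and SAP 2.4.5 sends laboratory parameters that are efficacy endpoints to Section 2.4.4. This stands in part. By-visit creatinine is clearly covered. For eGFR the text is mixed: SAP 2.4.5.4 names it for laboratory graphs and gives it abnormality categories, and the paragraph just before the averaging rule speaks of efficacy analyses too. A reader might infer that the efficacy eGFR change and the >50% decline counts are certainly averaged. The documents do not settle that.

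**The tie rule.** SAP 2.5.4 also says that the last measurement is taken when two are equally close to the target day. A reader might infer that the post-dose value would replace the pre-dose one in the efficacy tables. The tie rule follows the Step 2 windows, which re-allocate unscheduled results when a visit has none. A patient sampled at an attended scheduled visit never reaches Step 2, so this inference fails.

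**Who is affected.** It would be too strong to say that the Week 26 and 52 summaries simply become pre/post-dose averages. Only patients with both samples are affected, and the group shift is diluted accordingly. This stands.

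**Materiality.** Size and direction are unknown, and a shift shared by all arms changes the time trend rather than the contrast, provided that the paired shares are similar. Protocol 9.2 equates 15 days with about 5 half-lives, so one half-life is about 15/5 = 3 days. The pre-dose sample is thus itself on-drug, which may limit any between-arm effect. This supports a low severity. It does not remove the gap in the rule.

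**Intent.** The rule was probably meant for repeat tests, but the SAP does not say so, and it does separate nominal times for PK.

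**Conclusion.** The point holds in limited form and is minor. As written, SAP 2.5.4 merges pre-dose and 3-hour creatinine at Weeks 26 and 52 for patients with both samples. This affects by-visit creatinine summaries, and eGFR graphs or summaries where SAP 2.4.5.4 applies. Its reach to the efficacy eGFR tables and the >50% decline counts is unclear.

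The size rests on the assumed -10% to +10% acute change and on the share of paired samples; neither is in the documents. Within that assumption, an affected patient's creatinine shifts by at most 5% in either direction and eGFR by about +6.5% to -5.5%.

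A reader might infer that a treatment comparison is biased. The documents do not show this: an effect on the contrast needs a drug-specific acute change, or paired shares that differ between arms. The last on-treatment value is not part of the point, because the treatment epoch closes at the last administration. Nor are counts of clinically significant abnormalities, which use individual evaluations. All affected outputs are descriptive. HbA1c and the testing hierarchy are unaffected.

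**What to change.** Add to SAP 2.5.4:

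- The planned 3-hour post-dose creatinine is excluded from same-date averaging.
- The pre-dose value is the visit value for creatinine and eGFR in by-visit, change-from-baseline and >50% decline outputs, in both safety and efficacy tables.
- The 3-hour value is summarised separately by nominal time, as SAP 2.4.6 does for PK.

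The samples are already planned, so no new data are needed. The cost is a sentence or two and one extra table. SAP 1.6 records that the first-step analysis was conducted and reported for top-line results, so this should be documented as a clarification made after that analysis. If Week 26 creatinine or eGFR was among those results, the CSR should state which value was used.
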